# **14.6 Laboratory Measurements**

Venous blood and urine samples will be collected from the subjects by a trained member of the clinical team. Consent will be collected from the subjects for use of these samples for the purposes of the proposed study.

Blood and urine samples are sent for laboratory testing in linked anonymised form (subject number, initials, and the subjects' gender and date of birth for analytical reasons). This information is able to be linked directly to the volunteer by the Quotient research team and study monitor, however not by the laboratory staff or sponsor.

Safety laboratory tests and virology will be carried out on blood samples, and drugs of abuse tests and urinalysis will be carried out on urine samples. The research will not involve analysis or use of human DNA.

Blood and urine samples results will be reviewed by a physician and acted upon before the subject is dosed or receives their next dose, or is released from the study, as is appropriate. A list of the laboratory parameters measured is presented in Appendix 1.

#### 14.6.1 Haematology, Clinical Chemistry and Coagulation

Laboratory tests will be performed by The Doctors Laboratory according to the time schedule presented in Appendix 2. Blood samples will be collected and processed as detailed in the Clinical Sample Processing Manual. Scheduled blood samples will be taken following an 8 h fast.

The acceptable deviations from the nominal blood sampling time points for laboratory assessments are:

- The pre-dose blood sample will be taken ≤2 h before dosing
- Post-dose blood samples will be taken ± 30 min from the nominal blood sampling time except when the time point coincides with the PK blood sampling time. In this situation, the time window for the PK sample applies.

CLcr will be calculated at screening for eligibility purposes and at the time points indicated in Appendix 2 by The Doctors Laboratory using the Cockcroft-Gault equation and body weight:

CLcr (mL/min) = (140-age [years]) x (body weight [kg]) (x 1.23) serum creatinine (µmol/L)

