• Severe non-serious adverse reactions (ie, severe non-serious AE considered as, at least possibly related to the IMP administration) occur in two subjects in the same cohort, independent of within or not within the same system organ class.

Or

- If two or more subjects in the pre-ceding dose group experience any of the following:
  - ALT or AST >3x upper limit of normal (ULN) and considered IMP related.
  - Decrease in CLcr below 80 mL/min and judged as clinically significant by the investigator (with reference to the change from baseline value) and considered IMP related.

 an absolute increase in serum creatinine of ≥0.3 mg/dL or ≥ 26.4 µmol/L which is judged as clinically significant and considered IMP related.

Or

- If one or more subjects in the preceding dose group experience:
  - an increase in Troponin I concentration > ULN which is considered clinically significant by the investigator (with reference to the change from baseline value) and considered IMP related.
  - an increase in QTcF value of >60 msec from baseline, confirmed by repeat triplicate measurements or an absolute increase in QTcF >500 msec, confirmed by repeat measurement and considered IMP related.

Or

 if the dose in a single subject is anticipated to exceed an AUC0-24 of ≥100 µg×h/mL. These limits are based on the exposure observed at the 20 mg/kg in cynomolgus monkeys (NOAEL; AUC0-24 of 101 µg×h/mL in male and 111 µg×h/mL in females).

Or

 if the dose in a single subject is anticipated to exceed a Cmax of ≥ 8.0 µg/mL. These limits are based on the exposure observed at the 20 mg/kg in cynomolgus monkeys (NOAEL; Cmax of 8.03 µg/mL in males and 9.03 µg/mL in females).

Dose escalation between cohorts will be limited to a maximal 5-fold increase for the first 3 cohorts and a maximal 3-fold increase thereafter, depending on safety and tolerability data and predicted exposure (both AUC and  $C_{max}$ ).

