#### 8.3 Subject Withdrawal

If a subject wishes to leave the study at any time, they will be permitted to do so. Every reasonable effort will be made by Quotient Sciences to complete a final assessment/discharge procedures. Quotient Sciences will advise the sponsor of the withdrawal of any subject from the study.

Early withdrawal is defined as the date of the decision to withdraw the subject from the study. Subject completion is defined as the date of the last procedure conducted or last contact (ie phone call) for that subject.

If a subject requests to leave the clinical unit earlier than the planned discharge time eg due to unforeseen personal circumstances, but aims to return to the clinical unit to complete the study, this will be documented as a subject self-discharge and a protocol deviation. The subject must complete the planned assessments/discharge procedures before discharge from the clinical unit and will return for the next assessments, as planned.

Subjects will be withdrawn from the study drug(s) for the following reasons:

- Experiencing a serious or severe AE including but not limited to:
  - QTcF interval of >500 msec or increase in QTcF interval of >60 msec from baseline (confirmed following a repeat ECG after 10 min in resting position)
  - ALT concentration >3 × the upper limit of the reference range (confirmed following a repeat ALT blood test)
- Experiencing a 25% decrease in CLcr
- Pregnancy
- Concurrent illness or requirement for prohibited medication
- At the discretion of the investigator

Subjects will be withdrawn from the study for the following reasons:

- Termination of the study
- Upon the subject's request (withdrawal of consent)
- Significant deviation from the protocol

For the purpose of QTcF withdrawal criteria, baseline will be considered as the average of the pre-dose Day 1 triplicate measurement. For the purpose of CLcr and ALT withdrawal criteria, baseline will be considered as the admission Day -1 measurement.

For a subject who withdraws because of an IMP-related AE, every effort will be made to ensure the subject completes follow-up procedures. Any subject withdrawn or discontinuing the study prematurely because of an IMP-related AE or termination of the study will be considered to have completed the study, and will not be replaced.

Subjects withdrawing for other reasons may be replaced at the discretion of the investigator and sponsor.

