#### 9.2 Inclusion Criteria

- 1. Healthy males (Cohorts 1 to 7) or healthy WONCBP (Cohort 8)
- 2. 18 to 55 years (Cohorts 1 to 7) or 18 to 60 years (Cohort 8) of age at the time of signing informed consent
- 3. Body mass index (BMI) of 18.0 to 30.1 kg/m^2 as measured at screening
- 4. General good physical health determined by medical and surgical history, physical examination, 12-lead ECG, vital signs and clinical laboratory tests

- 5. Normal blood pressure: Systolic blood pressure between ≥90 and ≤140 mmHg, Diastolic blood pressure ≤90 mmHg, measured after 10 min rest in supine position at screening, admission and pre-dose
- 6. A resting HR between ≥40 and ≤90 bpm measured after 10 min rest in supine position at screening, admission and pre-dose
- 7. ECG recording without clinically significant abnormality, including QTcF measure of ≤450 msec (male) or ≤470 msec (female) at screening, admission and pre-dose
- 8. Having had no febrile seizures or infectious illness for at least 7 days prior to administration of the IMP (Day 1)
- 9. Must be willing and able to communicate and participate in the whole study
- 10. Must provide written informed consent
- 11. Must agree to adhere to the contraception requirements defined in Section 9.4 and the life-style restrictions described in Section 9.6

Inclusion criteria 4, 5, 6, 7 and 8 from the list above will be re-assessed at admission/pre-dose.

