#### 9.3 Exclusion Criteria

- 1. Subjects who have received any IMP in a clinical research study within the 3 months or 90 days prior to Day 1
- 2. Subjects who are study site employees, or immediate family members of a study site or sponsor employee
- 3. Subjects who have previously been enrolled in this study and/or have received DNDI-0690 previously
- 4. History of any drug or alcohol abuse in the past 2 years
- 5. Demonstrating excess in caffeine/xanthine consumption (more than 6 cups of coffee or equivalent a day)
- Regular alcohol consumption in males >21 units per week and females >14 units per week (1 unit = ½ pint beer, or a 25 mL shot of 40% spirit, 1.5 to 2 Units = 125 mL glass of wine, depending on type). As confirmed by a positive alcohol breath test at screening or admission
- Current smokers and those who have smoked within the last 12 months. As confirmed by a breath carbon monoxide reading of greater than 10 ppm at screening or admission
- 8. Current users of e-cigarettes and nicotine replacement products and those who have used these products within the last 12 months
- 9. Females of childbearing potential including those who are pregnant or lactating (all female subjects must have a negative serum pregnancy test at screening and admission). A woman is considered of childbearing potential unless she is permanently sterile (hysterectomy, bilateral salpingectomy, bilateral tubal ligation, bilateral tubal occlusion and bilateral oophorectomy) or is postmenopausal (had no menses for 12 months without an alternative medical cause and a serum follicle stimulating hormone [FSH] concentration ≥40 IU/L)
- 10. Subjects who do not have suitable veins for multiple venepunctures/cannulation as assessed by the investigator or delegate at screening
- 11. Clinically significant abnormal biochemistry, haematology, coagulation or urinalysis (especially AST, ALT, gamma glutamyl transpeptidase [GGT], ALP, creatinine, and BUN) as judged by the investigator (laboratory parameters are listed in Appendix 1). Subjects with Gilbert's syndrome are allowed
- 12. Confirmed positive drugs of abuse test result (drugs of abuse tests are listed in Appendix 1)

- 13. Positive hepatitis B surface antigen (HBsAg), hepatitis C virus antibody (HCV Ab) or human immunodeficiency virus (HIV) results
- 14. Evidence of renal impairment at screening or admission, as indicated by an estimated CLcr of <80 mL/min using the Cockcroft-Gault equation

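### The printed Cockcroft-Gault formula has one constant (1.23) and no female term; used as printed it would overstate CLcr in the all-female Cohort 8 by about 17 to 18%

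*Protocol*

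**What the plan says.** Protocol Section 14.6.1 assigns the calculation to the central laboratory: "CLcr will be calculated at screening for eligibility purposes and at the time points indicated in Appendix 2 by The Doctors Laboratory". It names the Cockcroft-Gault equation with body weight and then prints a single formula, "140-age [years]) x (body weight [kg]) (x 1.23", with serum creatinine in µmol/L as the divisor. The formula has no sex term and is not restricted to any cohort.

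The population is of both sexes. Section 9.2 admits "Healthy males (Cohorts 1 to 7) or healthy WONCBP (Cohort 8"), with ages "18 to 55 years (Cohorts 1 to 7) or 18 to 60 years (Cohort 8) of age".

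The resulting CLcr is used in four places:

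- Section 9.3, exclusion criterion 14, at screening or admission: "an estimated CLcr of <80 mL/min using the Cockcroft-Gault equation". The limit is the same for both sexes.
- Section 8.2.1, as one of the criteria against dose escalation: "Decrease in CLcr below 80 mL/min and judged as clinically significant by the investigator". Relation to the product and at least two affected subjects are also required.
- Section 8.3, as a withdrawal criterion: "Experiencing a 25% decrease in CLcr".
- Section 7.2.1, where CLcr is one of three renal parameters singled out in the primary endpoint.

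Section 9.3, Appendix 1 and the safety-laboratory footnote to Appendix 2 refer to the equation by name only. None supplies a female constant.

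**The concern.** The protocol names one equation but prints only its male form, in a document that has a female cohort. Other limits do distinguish the sexes, for example the QTcF limits in Section 9.2 and the alcohol limits in Section 9.3. The CLcr formula does not.

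Two things are at stake. The first is eligibility. Section 6.4 names the kidney as a target organ in monkeys and relies on excluding subjects with impaired renal function. If the formula is applied as printed, women whose CLcr by the sex-specific equation is below 80 mL/min could pass criterion 14. Cohort 8 extends to age 60, and a higher age lowers the estimate, so values near the limit are plausible.

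The second is reporting. Section 15.4 summarises safety data by dose level, for all active subjects combined and for all placebo subjects combined. Female values and mL/min changes on an inflated scale would stand beside the men's, or be pooled with them. Sections 6.1 and 6.3 give similarity of safety in women and men as a reason for including women.

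**Working it through.** **Inputs from the protocol.** Constant 1.23 with creatinine in µmol/L (Section 14.6.1); limit 80 mL/min (Sections 8.2.1 and 9.3); Cohort 8 all female, 8 subjects planned and at most 2 replacements (Sections 8.4 and 9.2).

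**Assumption, not in the protocol.** The named equation carries a female factor of 0.85. I take the female constant as 1.04 to 1.05, according to rounding.

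**Reproducing the printed constant.** Converting the usual mg/dL form of the equation (divisor 72) to µmol/L gives 88.4/72 = 1.228, which rounds to 1.23. The printed constant is therefore correct for men. The female equivalent is 0.85 × 1.228 = 1.044, or 0.85 × 1.23 = 1.0455.

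**Size of the overestimate.** Age, weight and creatinine cancel, so the ratio of printed to sex-specific CLcr is 1.23/k, and a printed 80 mL/min corresponds to 80 × k/1.23.

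| Female constant k | 1.23/k | Overestimate | Printed 80 mL/min corresponds to |
|---|---|---|---|
| 1.04 | 1.183 | 18.3% | 67.6 mL/min |
| 1.0455 | 1.176 | 17.6% | 68.0 mL/min |
| 1.05 | 1.171 | 17.1% | 68.3 mL/min |

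Conversely, a sex-specific value of 80 mL/min prints as 80 × 1.23/1.04 = 94.6, or 80 × 1.23/1.05 = 93.7. Women with printed values from 80 to about 94 mL/min are the ones whose eligibility would change.

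**Constructed example (not trial data).** For a woman aged 60, 60 kg, creatinine 70 µmol/L:

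- as printed: (140 − 60) × 60 × 1.23/70 = 84.3 mL/min, not excluded;
- with 1.04: (140 − 60) × 60 × 1.04/70 = 71.3 mL/min, excluded;
- with 1.05: (140 − 60) × 60 × 1.05/70 = 72.0 mL/min, excluded.

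**What is not affected.** With age and weight fixed, a relative change depends on creatinine alone. A rise from 75 to 100 µmol/L gives 75/100 = 0.75, a 25% fall, with either constant. The withdrawal rule and percent changes from baseline therefore stand. The absolute serum creatinine criterion in Section 8.2.1 does not use the formula.

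**Dose escalation.** The 80 mL/min criterion shifts by the same factor for women. But Cohort 8 is the last planned cohort, Section 8.2.1 caps its dose at the maximum tolerated in males, and the criterion also needs two subjects, clinical significance and relation to the product. It has little left to decide.

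**The case against.** The strongest reply is that the protocol names the Cockcroft-Gault equation, that Section 14.6 has gender and date of birth sent with samples for analytical reasons, and that the laboratory may therefore already use the sex-specific form. This stands as a limit on certainty. A reader might infer from the printed line that Cohort 8 values are in fact about 18% too high, or that women below the limit are in fact being enrolled. The document does not support that: it does not show how the laboratory computes CLcr. It does not remove the point either, because no section says that gender enters the calculation. If it does, the printed formula disagrees with practice.

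Second, the constant sits in its own brackets, which might mean that it applies to men only. The text does not say so, and that reading would give women a factor of 1.0, about 4 to 5% too low (1.0/1.04 = 0.96; 1.0/1.05 = 0.95). Neither reading is right for women. The missing fraction bar is probably an effect of reading the PDF and is not counted.

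Third, the female factor is external to the protocol. That is correct, and it is why a range is given.

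Fourth, other safeguards exist: exclusion criteria 11 and 15 cover clinically significant creatinine or BUN abnormalities and renal history, and serum cystatin C is measured with every safety panel. The planned statistical comparison of the sexes covers AUC and Cmax only. These points reduce the consequence; they do not make the formula correct.

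**Conclusion.** The point holds in a conditional form. Section 14.6.1 prints a formula that is right for men and is applied without qualification to a female cohort. If it is used literally, and if the female factor is 0.85, CLcr in Cohort 8 is overestimated by 17.1 to 18.3%, and the 80 mL/min exclusion limit acts at about 68 mL/min for women. Eight women are affected, or up to ten with replacements.

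The consequences are confined to criterion 14 at screening and admission, and to absolute CLcr values and mL/min changes for women in the primary safety summaries. A reader might also infer that dose-escalation decisions are compromised. The documents do not support that, given the position and dose cap of Cohort 8 and the further conditions on the criterion. Nor does the point question the 80 mL/min limit; it concerns only the value that is compared with it.

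**What to change.** In Section 14.6.1, print the formula with a constant for each sex, 1.23 for men and 1.23 × 0.85 (about 1.04 to 1.05, with the rounding fixed) for women, so that it agrees with the equation named in Section 9.3 and the appendices. Confirm with the laboratory which form it uses. Recompute any Cohort 8 screening, admission or later values already produced with 1.23, and recheck criterion 14 against them. Leave the 80 mL/min limit unchanged.

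The cost is one line of protocol text and one query to the laboratory, plus a small recalculation if 1.23 was used. The downside is that some women near the limit may fail screening; the protocol has no data from which to say how many.

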# 14.6.2 Urinalysis

Urinalysis will be performed on-site using a dipstick according to the time schedule presented in Appendix 2. Urine samples will be collected and processed as detailed in the Clinical Sample Processing Manual. Any urine used for urinalysis will be added back to the full sample for PK analysis. If microscopy is required, a urine sample (approximately 20 mL) will be taken from the urine PK collection, after the sample has been weighed and sent to The Doctors Laboratory.

The acceptable deviations from the nominal urine sampling time points for urinalysis are:

• Post-dose urine samples will be taken ± 2 h from the nominal urine sampling time

# 14.6.3 Pregnancy Test

Serum and urine pregnancy tests will be performed as detailed in Appendix 2. The samples will be collected and processed as detailed in the Clinical Sample Processing Manual.

#### 14.6.4 Follicle-Stimulating Hormone Test (for Post-menopausal Females Only)

Serum FSH tests will be performed as detailed in Appendix 2. The samples will be collected and processed as detailed in the Clinical Sample Processing Manual.

#### 14.6.5 Drug Screen

A urine drug screen will be performed on-site using a dipstick method according to the time schedule presented in Appendix 2. The sample will be collected and processed as detailed in the Clinical Sample Processing Manual. Subjects will be screened for the drugs of abuse listed in Appendix 1.

#### 14.6.6 Alcohol Breath Test

An alcohol breath test will be performed according to the time schedule presented in Appendix 2. A positive result will exclude the subject from dosing during that admission.

#### 14.6.7 Carbon Monoxide Breath Test

A carbon monoxide breath test will be performed according to the time schedule presented in Appendix 2. A result of greater than 10 ppm will exclude the subject from dosing during that admission.

#### 14.6.8 Troponin I

Serum samples for Troponin I will be collected at the time points indicated in Appendix 2. Time points for sample collection may be altered based on emerging data, see Section 8.2.1.

# 14.6.9 Abnormal Laboratory Findings

In cases where laboratory findings are outside the normal range and the investigator believes that the results may be of clinical significance, repeat sampling may be requested as clinically indicated. If the abnormal finding is clinically significant, appropriate actions will be taken eg, the subject will not be entered into the study or the subject may be withdrawn from the study drug. The subject will be referred to their GP or other appropriate provider for further care. The same will apply if the results of the HBsAg, HCV Ab or HIV test are positive and in addition the investigator will ensure that adequate counselling is available if requested.

Abnormal results at follow-up assessments will also require repeat testing if the investigator believes the results may be of clinical significance.

Any clinically significant abnormality, including changes from baseline, must be reported as an AE.

Additional blood and/or urine samples may be taken for safety tests. Furthermore, additional assays outside those specified in the protocol may be performed for safety reasons as requested by the investigator.

#### 14.7 Vital Signs Measurements

Blood pressure and HR will be measured by an automated recorder after the subject has been in a supine position for a minimum of 10 min according to the time schedule presented in Appendix 2. Where possible the same arm will be used for all blood pressure measurements. Should the designated arm need to be changed due to, for example, re-cannulation, this will not be classed as a protocol deviation. Tympanic body temperature will be measured at screening and pre-dose only. The acceptable deviations from the nominal vital signs measurement time points are:

- The pre-dose vital signs measurements will be taken ≤2 h before dosing.
- Post-dose vital signs measurements will be taken ± 15 min from the nominal post-dose time points.
- Discharge vital signs measurements will be taken ± 1 h from the nominal time point.

If a subject shows an abnormal assessment at any stage, repeat measurements may be made and the abnormality followed to resolution if required. Additional measurements may be taken as deemed necessary by the investigator.

Any clinically significant abnormality, including changes from baseline, must be reported as an AE.

#### 14.8 ECG Measurements

12-lead ECGs will be measured after the subject has been in the supine position for a minimum of 10 min according to the time schedule presented in Appendix 2. ECGs will be taken in triplicate at pre-dose (for baseline), all post-dose measurements will be taken as a single ECG. The acceptable deviations from the nominal ECG measurement time points are:

- The pre-dose ECG measurements will be taken ≤2 h before dosing
- Post-dose ECG measurements will be taken ± 15 min from the nominal post-dose time point.

• Discharge ECG measurements will be taken ± 1 h from the nominal time point.

If a subject shows an abnormal assessment at any stage, repeat measurements may be made and the abnormality followed to resolution if required. Additional measurements may be taken as deemed necessary by the investigator or sub-investigator. The PI or sub-investigator must double-check the results.

All safety ECG (from baseline to end of study visit) will be sent to the central ECG reading facility (Banook) for review by the cardiologist. A cohort report on ECG findings will be issued for review at the SRC dose-escalation meetings. Measurements will be sent back to Quotient at the end of the study.

Any clinically significant abnormality, including changes from baseline, will be reported as an AE.

